8. STUDY PROCEDURES/EVALUATIONS

8.1 Scheduled Study Visits

8.1.1 Screening Visit

- Informed consent
- Screening inclusion/exclusion criteria
- Demographics
- Distribute study toothbrush, toothpaste and dental floss to use for washout (at least 7-days)

8.1.2 Baseline Visit

- Baseline inclusion/exclusion criteria
- Randomization
- Concomitant medications
- Subject blinding assessment
- Löe-Silness Gingival Index
- Modified Quigley-Hein Plaque Index
- Eastman Interdental Bleeding Index
- Dental prophylaxis
- Test products distribution and training
- Oral hard and soft tissue evaluation (Oral Exam)
- Subject diary, instructions and return appointment
- Adverse events, protocol deviations (if applicable)

8.1.3 Interim Visit (approximately 1.5 months)

- Review of subject diary and visual inspection of product use/compliance
- Replenish study products
- Reinforcement of product use instructions
- Concomitant medications
- Adverse events, protocol deviations (if applicable)

8.1.4 3-Month Visit (\pm 10 days)

- Any change in medical/dental history
- Concomitant medications
- Oral hard and soft tissue evaluation (Oral Exam)
- Löe-Silness Gingival Index
- Modified Quigley-Hein Plaque Index
- Eastman Interdental Bleeding Index
- Review of subject diary and visual inspection of product use/compliance
- Replenish study products
- Reinforcement of product use instructions

- Adverse events, protocol deviations (if applicable)

8.1.5 Interim Visit (approximately 4.5 months)

- Review of subject diary and visual inspection of product use/compliance
- Replenish study products
- Reinforcement of product use instructions
- Concomitant medications

8.1.6 End of Study visit or 6-Month Visit (\pm 10 days)

- Any change in medical/dental history
- Concomitant medications
- Subject blinding assessment
- Oral hard and soft tissue evaluation (Oral Exam)
- Loe-Silness Gingival Index
- Modified Quigley-Hein Plaque Index
- Eastman Interdental Bleeding Index
- Review of subject diary and visual inspection of product use/compliance
- Adverse events, protocol deviations (if applicable)
- Collection of study products

8.2 Study Procedures

8.2.1 Screening Visit

Prior to entering the study, the Investigator/Study Coordinator or designated assistant will explain to each subject the elements of informed consent including, nature of the study, the purpose, procedures and expected duration; and the benefits and possible risks involved in study participation.

A screening oral examination will be conducted to determine study eligibility. If eligible, subjects will be scheduled for the baseline visit and they will receive the study toothpaste, tooth brush and dental floss for the washout period. Subjects will be instructed not to brush or floss their teeth after 10:00 pm the night before assessments and not to eat and drink for 4 hours prior to the scheduled clinical examinations.

8.2.2 Baseline Visit

The clinical examinations will be conducted by calibrated examiners. The same examiner will perform the same clinical examination throughout the study. See Appendix 17.2 on training and calibration procedures of the clinical examiners. A subject blinding assessment question will be completed at the baseline visit after the first dose is taken. Professional cleaning by a dental hygienist will be completed at end of the baseline visit so all subjects start the study with a plaque free status.

8.2.3 Assessment of Efficacy Methods

8.2.3.1 Oral Tissue Examination

The oral hard and soft tissue examination findings will be recorded as normal (oral tissue is what is expected by visual inspection) or abnormal. Hard tissue is defined as the visible tooth surface above the gum line (gingival area). Soft tissue refers to gingiva, oral mucosa and tongue. All abnormal findings will be described on the case report form. Examples of abnormal oral clinical findings:

Hard tissue: changes including discoloration/staining, erosion, white spots etc.

Soft tissue: changes in gingiva, oral mucosa, tongue, swelling and redness (inflammation), vesicles, ulcers, desquamation, white or red lesions, fungal overgrowth or bleeding tissue.

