9.3 Soft and Hard Oral Tissue Assessment

The incidence of normal and abnormal soft and hard tissue findings will be summarized by visit and treatment group. Shifts in findings from normal/abnormal to normal/abnormal observed within the first 3 months will be summarized by treatment group. The worst assessment up to the 3-month visit will be used in this summary. In addition, shifts in findings from normal/abnormal to normal/abnormal between the baseline visit and the last available visit will be summarized by treatment group.

Revision History

Revision Details:

- 1 To establish statistical analysis plan before study enrollment.
- 2
 - (1) To clarify when per protocol dataset will be applied (Section 5.3).
 - (2) To clarify dosing compliance computation (Section 7.4)
 - (3) To indicate the classification of AEs using the MedDRA dictionary (Section 9.1)
 - (4) To clarify the incorporation of the unscheduled oral assessment data in planned summaries (Section 9.3).

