6.3 Baseline Inclusion Criteria at Enrollment

Subjects who meet the screening inclusion criteria and the following baseline inclusion criteria apply will be eligible for treatment randomization:

- Completed the washout period (at least 7 days) using only the study toothbrush, dental floss and toothpaste
- A qualifying baseline Gingival Index of at least 1.0, as determined by the Löe-Silness Gingival Index (GI)
- A qualifying baseline Modified Quigley-Hein (Lobene-Soparkar Modification of Turesky's Modification) Plaque Index (PI) of at least 1.5 (referred to as Modified Quigley-Hein Plaque Index in the following text)

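### The soft-tissue normal/abnormal summaries in SAP 9.3 may be uninformative for new oral harm, because qualifying gingivitis can already count as abnormal at baseline and no rule separates it

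*Combined protocol and SAP*

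**What the plan says.** Protocol 8.2.3.1 has examiners classify hard and soft tissue findings, "recorded as normal (oral tissue is what is expected by visual inspection) or abnormal". On scope it says "Soft tissue refers to gingiva, oral mucosa and tongue". Its examples of abnormal findings include "Soft tissue: changes in gingiva, oral mucosa, tongue, swelling and redness (inflammation), vesicles, ulcers, desquamation, white or red lesions", and the list goes on to fungal overgrowth and bleeding tissue. Each abnormal finding must also be described on the case report form.

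Protocol 6.3 requires a mean Löe-Silness GI of at least 1.0 at baseline. Protocol 8.2.3.2 defines every grade above 0 as some degree of inflammation. Grade 1 is a slight colour change; redness and edema enter at grade 2.

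SAP 9.3 summarizes the incidence of normal and abnormal findings by visit, and shifts within the first 3 months using the worst assessment in that period. In addition, "shifts in findings from normal/abnormal to normal/abnormal between the baseline visit and the last available visit will be summarized by treatment group". It plans no count of new or worsened findings, no breakdown by lesion type, and no rule for gingivitis present at entry.

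Tracking abnormal tissue change is a stated safety objective (protocol 5.5, SAP 2.2). Protocol 11.6 makes abnormal tissue a safety variable with a four-group test, followed by test rinse versus vehicle if that test is significant.

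**The concern.** The abnormal examples overlap with the disease that the trial enrols. Gross soft-tissue pathology is excluded at screening (protocol 6.2), so gingivitis is the main abnormality left at baseline. Two things follow if examiners rate it abnormal.

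First, a two-level rating has nothing worse than abnormal. A subject abnormal for gingivitis who develops an ulcer, desquamation or fungal overgrowth shows no shift, and taking the worst assessment up to 3 months does not help. Mucosal sloughing and irritation are named risks in protocol 4.4.1, so this is the kind of harm the summary should show.

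Second, efficacy enters the safety table. If the rinse reduces gingivitis, abnormal-to-normal shifts and a falling incidence of abnormal findings partly restate the GI result.

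If examiners differ in how they treat gingivitis, the summary mixes both meanings. The calibration in protocol Appendix 2 covers GI and PI only, so it does not standardize this judgement.

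**Working it through.** **The plan's own figure.** No figure is attached to the tissue summaries. The one design calculation is the sample size (protocol 11.8, SAP 6.1). With a difference of 0.40, SD 0.5 and one-sided alpha 0.025, a two-sample t-test has 90.2% power at 34 per group and 89.3% at 33, so the stated 34 reproduces. It is not in dispute; only the 50 recruited per arm is used below.

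**Step 1: how much inflammation entry implies.** A subject's GI is the mean over scored surfaces. Let p be the share of surfaces scoring above 0 and g the highest grade present. Then mean GI ≤ g × p, and a mean of at least 1.0 requires p ≥ 1/g.

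- g = 3: p ≥ 1/3, which is 168/3 = 56 surfaces with 28 scored teeth, or 120/3 = 40 with 20.
- g = 2: p ≥ 1/2, which is 84 of 168 or 60 of 120.
- g = 1: p = 1, every surface at grade 1.

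Every eligible subject therefore has gingival inflammation as the GI defines it. This does not show that every subject would be rated abnormal at the oral exam.

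**Step 2: what the shift summary shows under each reading of protocol 8.2.3.1** (one soft-tissue rating per subject).

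| Event after baseline | Gingivitis rated abnormal | Gingivitis rated as expected (normal) |
|---|---|---|
| New ulcer or desquamation | abnormal to abnormal | normal to abnormal |
| Gingivitis resolves, no lesion | abnormal to normal | normal to normal |
| No change | abnormal to abnormal | normal to normal |

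In the middle column, new harm and no change fall in the same cell. The text does not say which column applies.

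**Step 3: illustration of size.** Assumptions that are not in the documents: a share b of each arm is normal at baseline; a new lesion arises in 10% of subjects (fourth column); new abnormality arises in 25% versus 5% (last column). There is one composite rating per subject and 50 per arm with no dropout. The number able to shift is m = 50b. The chance of seeing at least one shift in an arm is 1 − 0.9^m; for m = 25 that is 1 − 0.9^25 = 0.93. The last column is the power of Fisher's exact test at two-sided 0.05 with m per arm.

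| b | 50b | m | At least one shift, 10% rate | Power, 25% vs 5% |
|---|---|---|---|---|
| 100% | 50 | 50 | 99% | 75% |
| 50% | 25 | 25 | 93% | 37% |
| 25% | 12.5 | 12 | 72% | 9% |
| 10% | 5 | 5 | 41% | 1% |
| 0% | 0 | 0 | 0% | 0% |

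**The case against.** The strongest reply is that new oral harm is recorded elsewhere. Adverse event incidence is the principal safety measure (protocol 9.1). Events can be found by the examiner's visual inspection, and mucosal sloughing is a listed example (protocol 9.3). Events are coded, listed verbatim and compared across arms (SAP 9.1), diary side effects are summarized weekly and tested (SAP 9.2), and abnormal findings are described on the case report form. All of this stands. It confines the problem to one summary, but tissue change is a separate safety objective, and SAP 9.3 does not plan to use the descriptions.

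A reader might infer four stronger things that the documents do not support.

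- *That every subject is abnormal at baseline.* Normal means expected on inspection, and an examiner may regard ordinary gingivitis as expected. A mean GI of 1.0 can also consist wholly of grade 1, which need not be recorded as redness or swelling. The baseline category is undefined, not known.
- *That gingivitis masks lesions at all sites.* The layout of the case report form is not in the documents. If gingiva, mucosa and tongue are rated separately, masking is confined to the gingiva.
- *That improving gingivitis cancels mucosal harm.* In a shift table the two directions are separate cells and no netting is planned. Only the by-visit incidence blends them.
- *That staining is masked too.* Protocol 8.2.3.1 lists "Hard tissue: changes including discoloration/staining, erosion, white spots etc", and protocol 8.2.2 says "Professional cleaning by a dental hygienist will be completed at end of the baseline visit". Masking would need the oral exam to precede the cleaning, and that order is not fixed. Protocol 8.1.2 lists the exam after the prophylaxis, although the list is not clearly chronological: it puts randomization before the index scoring that decides eligibility. The cleaning is meant to leave teeth free of plaque, which does not mean free of stain. GI entry has no bearing on tooth surfaces.

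**Conclusion.** The point holds in a limited form. The soft-tissue normal/abnormal summaries in SAP 9.3 may be uninformative for new harm, because qualifying gingivitis fits the abnormal examples, could equally be called expected, and no rule decides. To say that the tables cannot show new oral harm would go too far, for the reasons given above.

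What is certain is that every eligible subject has at least one third of scored surfaces inflamed by the GI's definition. The loss in the shift summary ranges from nothing, if all 50 per arm are rated normal at baseline, to complete, if none are. That range assumes one composite soft-tissue rating per subject, and the documents do not narrow it. The primary and secondary efficacy analyses are unaffected. Severity is minor and confidence moderate.

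**What to change.** In protocol 8.2.3.1, state how qualifying plaque-associated gingivitis is classified at the oral exam, and apply that rule in the same way at every visit.

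In SAP 9.3, add as the main tabulation the number of subjects per arm with any new or worsened finding relative to the baseline description. Present it by tissue (gingiva, mucosa, tongue, hard tissue) and by type, using the descriptions already required on the case report form. Keep gingival findings as their own row, so that rinse-related irritation is not hidden by setting gingivitis aside. Judge staining against the baseline description; do not count all stain seen after baseline as new. Keep the normal/abnormal shift table as supportive.

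The cost is protocol and SAP wording, some coding of free-text descriptions, and judgement on gingival findings, best made before unblinding. No visit, procedure or measurement is added.

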8.2.3.2 Gingival Index

The method of Löe-Silness will be used for evaluating gingivitis according to the following criteria:^{7,8}

Löe-Silness Gingival Index

0 = Absence of inflammation.

1 = Mild inflammation: slight change in color and little change in texture.

2 = Moderate inflammation: moderate glazing, redness, edema, hypertrophy. Tendency to bleed upon probing.

3 = Severe inflammation: marked redness and hypertrophy. Tendency to spontaneous bleeding.

The gingival surface surrounding each tooth (all natural teeth) will be scored on six surfaces: 1) mesio-facial; 2) mid-facial; 3) disto-facial; 4) mesio-lingual; 5) mid-lingual; and 6) disto-lingual.

Third molars and those teeth with cervical restorations or prosthetic crowns will be excluded from the scoring procedure. The GI score of the individual can be obtained by adding the scores of all surfaces and dividing by the number of surfaces examined.

8.2.3.3 Plaque Index

The Lobene-Soparkar modification of Turesky's modified Quigley-Hein Plaque Index will be used for evaluating dental plaque according to the following criteria:^{9,10,11}

Modified Quigley-Hein Plaque Index

0 = No plaque

1 = Separate flecks of plaque at the cervical margin of the tooth

2 = A thin, continuous band of plaque (up to one mm) at the cervical margin of the tooth.

3 = A band of plaque wider than 1 mm, but covering less than 1/3 of the crown of the tooth.

4 = Plaque covering at least 1/3, but less than 2/3 of the crown of the tooth.

5 = Plaque covering 2/3 or more of the crown of the tooth.

Prior to examination, Vaseline will be applied to the subject's lips, a plaque disclosing solution is put into a medicine cup and a cotton tip applicator is used to apply solution to all surfaces of teeth. The subject's mouth is then rinsed with water and the examiner then records the plaque index.

Each tooth is scored for supragingival plaque on six surfaces: 1) mesio-facial; 2) mid-facial; 3) disto-facial; 4) mesio-lingual; 5) mid-lingual; and 6) disto-lingual. Third molars and those teeth with cervical restorations or prosthetic crowns will be excluded from the scoring procedure. The PI score of the individual can be obtained by adding the scores of all surfaces and dividing by the number of surfaces examined.

8.2.3.4 Bleeding Index

Gingival bleeding on probing will be examined using the Eastman Interdental Bleeding Index according to the following criteria and will be recorded on the case report form:¹² The Bleeding Index (BI) will determine the extent of interdental inflammation.

Eastman Interdental Bleeding Index

0 = Absence of bleeding.

1 = Presence of bleeding

The interdental cleaner is inserted between two teeth from the facial aspect, depressing the interdental tissues 1 to 2 mm. This is repeated four times and the presence or absence of bleeding within 15 seconds is recorded. The absence or presence of bleeding will be recorded for each examined site (between two teeth), and a score will be calculated as the number of bleeding sites out of the number of examined sites for each evaluation on a subject.

9. ASSESSMENT OF SAFETY

9.1 Safety Parameters

The principal measure of safety will be the incidence of adverse events reported during the study.

9.2 Unscheduled Visits

An unscheduled visit can occur any time during the study if the investigator believes the subject should be evaluated. The subjects will be instructed to notify the Study Coordinator or Principal Investigator with any medical/dental issues (cannot tolerate the rinse, oral issues, adverse events etc.) If the subject is requested to return to the clinic for an assessment/examination, this visit will be collected on the “unscheduled visit” form.

9.3 Adverse Events

An adverse event (AE) can be identified via visual examination by the dental examiner or reported by the subject. The Investigator is responsible for identifying AEs throughout the study. An AE may occur at any time during the conduct of the study, in any phase of the study or after the study is completed.

Examples of AEs that are considered expected during the conduct of the study include the following: mucosal sloughing, taste alteration, mouth or tongue numbness or tingling, and dry mouth. In addition, irritated or bleeding gums may occur due to probing during the dental examination.

9.3.1 Definitions

- Adverse event (AE) is any untoward medical occurrence, unintended disease or injury, or any untoward clinical sign (including a laboratory abnormality) in human subjects or users, whether or not considered related to the subject’s participation in the research.
- Serious Adverse Event (SAE) is an adverse event that results in death, is life-threatening, requires inpatient hospitalization or prolongation of existing hospitalization, results in disability or permanent damage, or results in congenital anomaly or birth defect. In addition, an AE may be considered a SAE if based on appropriate medical judgment,

may jeopardize the subject and may require medical or surgical intervention to prevent one of the above outcomes.

- Adverse Device Effect (ADE) is an AE that is considered by the Investigator to have a reasonable likelihood of being related to the use of the investigational device.
- Serious Adverse Device Effect (SADE) is an ADE that resulted in any of the consequences of an SAE.
- Unanticipated Adverse Device Effect (UADE) is any adverse device effect which by its nature, incidence, severity, or outcome was not previously identified in the protocol, clinical investigation plan, Investigator's Brochure, or risk analysis report.
- Unanticipated Serious Adverse Device Effect (USADE) is any serious adverse device effect which by its nature, severity or outcome was not previously identified in the protocol, clinical investigation plan, Investigator's Brochure, or risk analysis report, or any other unanticipated serious problem associated with a device that relates to rights, safety and welfare of subjects.

9.3.2 Recording and Reporting

The site personnel record each AE occurring in the study, including those not thought to be associated with the device, on the AE CRF. Documentation includes the AE description, severity, seriousness, date of onset and resolution, relationship to the investigational device, action taken and outcome.

If the AE is considered by the Investigator to be related to the study device, the event is considered an adverse device effect. The site personnel must promptly report all adverse device effects to the 3M study monitor. If the adverse device effect is also considered by the Investigator to be serious and/or unanticipated the Investigator must report it to the IRB as soon as possible and within 10 working days.

3M reports a serious, unanticipated adverse device effect to the FDA within 10 working days of notification.

10. CLINICAL MONITORING

The study monitor is responsible for ensuring the proper conduct of the study in regards to ethics, protocol adherence and data validity of the data recorded on the Case Report Forms (CRFs). The CRFs will be verified by the monitor at the study site at regular intervals throughout the study. The Investigator must allow the monitor and/or representative of the Sponsor, and any regulatory body to review and inspect the study files, patient medical records and other related study documents as required. CRFs will be reviewed for completeness and clarity. Missing or unclear data will be investigated by the monitor and will be clarified throughout the study.

In order to perform this role, the monitor must be given direct access to all subject's source documents (e.g., general charts, appointment books, enrollment and follow-up forms) that supports data on the CRFs. The study personnel must make available such records to monitor and to regulatory personnel for inspection including:

- Informed consent forms and HIPAA forms
- All study related IRB correspondence
- Protocol amendments, IRB approval
- Protocol deviations
- Accounting of all medical devices and other supplies
- Adverse events/adverse device effects

The progress of the study will be monitored by:

- EDC review
- Periodic on site visit
- Telephone communications
- Review of source documents

10.1 Monitor Training

The designated monitor will be qualified by experience including knowledge of Good Clinical Practices.

10.1.1 Site/Investigator Training

The Sponsor will be responsible for providing training to the investigator and appropriate clinical site study personnel.

11. STATISTICAL METHODS

11.1 General Statistical Considerations

Means and standard deviations will be calculated for all clinical measurements and assessments. Categorical variables will be summarized in frequency distributions. Analysis of variance (ANOVA) or (ANCOVA) will be used to test for treatment group differences between the subject groups over the visits. When appropriate, alternative statistical methods such as normalizing transformations or nonparametric tests may be used to analyze the data.

The GI, PI, and BI scores will be calculated as the average tooth score across all measures and teeth surfaces as one score per patient, per visit. For example, a patient with 28 evaluable teeth will have 168 data points (6 per tooth) averaged per tooth and then averaged over all teeth to

produce one score per patient per visit. The subject indices computed will range between 0 and 3 (GI), or 0 and 5 (PI), or 0 and 1 (BI).

All statistical analyses will be performed using SAS version 9.3 or above (SAS Institute, Cary, NC) or another statistical software package.

